5.1.5. Management of Adverse Effects Following Treatment with Cetuximab

5.1.5.1. Management of anaphylactic reaction following treatment with cetuximab

Patients who experience any grade anaphylactic reaction to cetuximab will be removed from the study.

5.1.5.2. Management of rash following treatment with cetuximab

A proactive and early approach to management of rash is crucial. Rash can be managed by a variety of treatment options to relieve symptoms and to reduce the rash. Advise patients to limit sun exposure during cetuximab treatment and for 2 months after the last dose of cetuximab. Advise patients to notify their healthcare provider of any sign of acne-like rash (which can include itchy, dry, scaly, or cracking skin and inflammation, infection or swelling at the base of the nails or loss of the nails), conjunctivitis, blepharitis, or decreased vision.

The recommendations for management are as follows:

General/Prevention:

- CTCAE v4.1 Grade 1 rash: mild rash may not need treatment. However, if treatment is considered necessary, topical hydrocortisone (1% or 2.5%) cream and/or clindamycin 1% gel can be used.
- CTCAE v4.1 Grade 2 rash: relief from major symptoms caused by CTCAE v4.1 Grade 2 skin-related adverse events should be achieved by a combination of local and systemic therapies including:
 - Systemic antibiotics (e.g., doxycycline or minocycline).
 - Topical treatment (e.g., hydrocortisone 2.5% cream, clindamycin 1% gel, pimecrolimus 1% cream).
 - Antihistamines (e.g., diphenhydramine).
 - Oral corticosteroids will not be allowed for the management of Grade 1 and 2 rash.
- CTCAE v4.1 Grade 3 (or greater) rash: may be treated in a manner similar to CTCAE v4.1 Grade 2 rash. In the event of CTCAE v4.1 Grade ≥ 3 rash, treatment with cetuximab should be paused until recovery to CTCAE v4.1 Grade ≤ 2. Treatment should be resumed at a reduced dose (see Section 4.3). If CTCAE v4.1 Grade ≥ 3 rash does not resolve to CTCAE v4.1 Grade ≤ 2 within 14 days of stopping cetuximab

Study Number: MCC 19178

treatment and despite optimal supportive care, the patient should not receive any further treatment with cetuximab.

5.2. NIVOLUMAB

5.2.1. Packaging, Labelling, and Storage

Please refer to the Investigators Brochure for detailed information. Medication numbers will be unique to each bottle and will be used for tracking purposes only.

5.2.2. Supply

Nivolumab is supplied in 100 mg, 10mg/ml solution in a single use vial. Vials will be supplied in quantities of 5 per carton.

5.2.3. Storage Conditions

Nivolumab must be stored in accordance with the instructions on the label.

5.2.4. Drug Accountability

Nivolumab is supplied by Bristol Myers Squibb.

The product storage manager should ensure that the study drug is stored in accordance with the environmental conditions (temperature, light, and humidity) as determined by BMS. If concerns regarding the quality or appearance of the study drug arise, the study drug should not be dispensed and contact BMS immediately.

Study drug not supplied by BMS will be stored in accordance with the package insert. Medication labeling for commercial supply is also available at https://dailymed.nlm.nih.gov/dailymed/index.cfm

Investigational product documentation (whether supplied by BMS or not) must be maintained that includes all processes required to ensure drug is accurately administered. This includes documentation of drug storage, administration and, as applicable, storage temperatures, reconstitution, and use of required processes (eg, required diluents, administration sets).

Infusion-related supplies (eg, IV bags, in-line filters, 0.9% NaCl solution) will not be supplied by Brystol-Myers Squibb and should be purchased locally if permitted by local regulations.

For nivolumab, please refer to the current version of the Investigator Brochures and/or pharmacy reference sheets for complete storage, handling, dispensing, and infusion information. The destruction of any unused investigational product should be performed according to institutional standards (Brystol-Myers Squibb will not be responsible for any drug destruction or accept any return drugs).

5.2.5. Management of Adverse Effects Following Treatment with Nivolumab

5.2.5.1. Management of immunological toxicities following treatment with nivolumab

A proactive and early approach to management of immunological toxicities is crucial. The toxicities can be managed by a variety of treatment options to relieve symptoms and to reduce the risk of worsening symptoms. **See Section 4.5.**

5.2.5.2. Management of non-immunological toxicities following treatment with nivolumab

IND#: Exempt

A proactive and early approach to management of immunological toxicities is crucial. The toxicities can be managed by a variety of treatment options to relieve symptoms and to reduce the risk of worsening symptoms. **See Section 4.5.**

5.3. TREATMENT COMPLIANCE

Records of study medications used, dosages administered, and intervals between visits will be recorded by study personnel.

6. ASSESSMENT OF EFFICACY

6.1. RECIST CRITERIA

Study Number: MCC 19178

To assess objective response, it is necessary to estimate the overall tumor burden at baseline to which subsequent measurements will be compared. Measurable disease is defined by the presence of at least one measurable lesion.

All measurements should be recorded in metric notation in centimeters. The same method of assessment and the same technique should be used to characterize each identified lesion at baseline and during follow-up. In cases where lesions are followed by clinical measurements, radiologic assessments should continue in accordance with the schedule of events to fully characterize the lesion(s). All baseline evaluations should be performed as closely as possible to the beginning of treatment and never more than 4 weeks before registration.

At baseline, tumor lesions will be characterized as either measurable or non-measurable.

6.1.1. Measureable Lesions

Measureable lesions should be selected on the basis of their size (those with the longest diameters) and their suitability for accurate repeated measurements. The sum of the longest diameters of all measurable lesions and shortest diameters of all measurable malignant lymph nodes will be calculated at baseline and reported as the baseline sum of longest diameters. The sum longest diameter will be used to characterize the objective overall tumor response. For lesions measurable in 2 or 3 dimensions, always report the longest diameter for tumors and the axis perpendicular to the longest axis for lymph nodes at the time of each assessment.

- Complete Response (CR): The disappearance of all measurable lesions.
- Partial Response (PR): At least a 30% decrease in the sum of the longest diameters of measureable lesions, taking as reference the baseline sum longest diameter.

- Progressive Disease (PD): At least a 20% increase in the sum of the longest diameters of target lesions, taking as reference the smallest sum longest diameter recorded since the baseline measurements, or the appearance of one or more new lesion(s).
- Stable Disease (SD): Neither sufficient shrinkage to qualify for partial response nor sufficient increase to qualify for progressive disease. To be assigned a status of stable disease, measurements must have met the stable disease criteria at least once after study entry at a minimum interval of 6 weeks.

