- ^{d.} Relevant medical history must include smoking status (current smoker, former smoker, never smoker), number of pack years, and year of smoking cessation. Relevant medical history will also include p16 status, if known. Historic radiologic assessments will also be accessed, in accordance with protocol section 6.2, to further characterize the disease under study and to contribute to exploratory objectives.
- ^{e.} CBC and diff (complete blood count and differential) include white blood cell count, absolute neutrophil count, hematocrit, hemoglobin, platelets, % lymphocytes, % monocytes, % neutrophils, other differentials. Safety labs may be collected up to 72 hours prior to dosing.
- f. Serum chemistries include a Complete Metabolic Panel (including Na, Cl, CO2, K, BUN, creatinine, Ca) AND Mg, Phos. Safety labs may be collected up to 72 hours prior to dosing.
- ^{g.} Liver function panel includes Alk Phos, total bilirubin, SGOT (AST), SGPT (ALT), total protein. Safety labs may be collected up to 72 hours prior to dosing.
- h. If tumor paraffin blocks (or sufficient slides) are not available, fresh biopsy will be obtained before the first treatment. If fresh biopsy is indicated, one core (or punch) will be collected in formalin and the second core (or punch) will be collected in liquid nitrogen. The end of treatment optional biopsy may be performed up to 30 days after the EOT visit as scheduling may require.
- ^{i.} Toxicity assessment: Common Terminology Criteria for Adverse Events (CTCAE) version 4.1 will be used. All toxicity grades (including grade 1) should be captured on the case report forms. All toxicities that occurred during treatment and until 30 days following completion of therapy should be followed until resolution.
- ¹ Tumor measurement: The same type of scan should be used for repeat measurements. The scans may be performed up to 7 days before the projected corresponding treatment visit. Scans in screening will include: CT- or MRI-neck, CT-chest, CT-abdomen, and CT-pelvis. Response scans can be limited to the anatomy of areas of known and suspected disease. Scans must be performed with contrast.

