- ^{k.} Pregnancy test should be done in women of childbearing age who are sexually active and may potentially be pregnant. Prior to study enrollment, women of childbearing potential must be advised of the importance of avoiding pregnancy during trial participation and the potential risk factors for an unintentional pregnancy. In addition, men enrolled on this study should understand the risks to any sexual partner of childbearing potential and should practice an effective method of birth control. All women of childbearing potential MUST have a negative pregnancy test within 7 days prior to enrollment. If the pregnancy test is positive, the patient must not receive investigational product and must not be enrolled in the study. In addition, all women of childbearing potential should be instructed to contact the Investigator immediately if they suspect they might be pregnant (e.g., missed or late menstrual period) at any time during study participation. The Investigator must immediately notify Moffitt Cancer Center and Lilly Oncology in the event of a confirmed pregnancy in a patient participating in the study.
- ^{I.} TSH required at the start of each cycle only (i.e. not required on day 15).
- m. The post-treatment research blood sample after getting the combination dose of cetuximab and nivolumab on C1D1 can be collected any time from Days 8 through 15 of Cycle 1 as long as it is collected prior to any study treatment of C1D15 cetuximab and nivolumab. A second post-treatment research blood sample is due on Cycle 4 Day 1 (or 3 months from C1D1 if off treatment).
- ^{n.} Radiology assessments every 6 weeks for Cycle 1-4 (i.e. C2D15, C4D1), then every 2 Cycles during Cycle 5-6 (i.e. C6D1) and then every 3 cycles during Cycle 7-24 (i.e. C9D1, C12D1, C15D1, C18D1, C21D1, C24D1) while on study drugs, and will include: CT- or MRI-neck, CT-chest, CT-abdomen, and CT-pelvis. Scans must be performed with contrast.
- o. Scans are only required at the end of treatment visit if not performed within 4 weeks prior.

IND#: Exempt

TABLE OF CONTENTS

		BREVIATIONS	—
		SYNOPSIS	
	HEMA		7
		T STUDY CALENDER	
TΑ	BLE OF (CONTENTS	10
1.	INT	RODUCTION	13
		ICAL BACKGROUND	
	1.1.1.	Treatment of Recurrent and/or Metastatic Head and Neck Squamous	Cell
		Carcinoma	13
	1.1.2.	The Role of Human Papillomavirus in HNSCC	13
		EGFR and Cetuximab in HNSCC	
	1.1.4.	PD-1 inhibitors in HNSCC	14
2.		TIONALE, OBJECTIVES, AND BENEFIT-RISK ASSESSMENT	
		IONALE FOR PERFORMING THE TRIAL	

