- Prior treatment with cetuximab or EGFR inhibitors given concurrently with radiation as a radiation sensitizer is included. However, cetuximab or EGFR inhibitors given in the recurrent and/or metastatic setting is NOT included.
- Patients must have measurable disease, defined as at least one lesion that can be accurately measured in at least one dimension (longest diameter to be recorded) as outlined in RECIST version 1.1.
- Patients must be ≥ 18 years of age.
- Life expectancy of greater than 3 months.
- ECOG performance status ≤ 2

Study Number: MCC 19178

- Patients must have normal organ function as defined below:
 - Absolute neutrophil count > 1,500/µL
 - Hemoglobin > 9 g/dL
 - Platelets > 100,000/µL
 - Total bilirubin ≤ 1.5 mg/dL X institutional upper limits of normal (ULN)
 - AST (SGOT)/ALT (SGPT) ≤ 3 X institutional ULN (or 5.0 X the ULN in the setting of liver metastasis)
 - Serum creatinine of ≤ 1.5 X ULN or creatinine clearance > 40 mL/minute (using Cockcroft/Gault formula): Female creatinine clearance = (140 age in years) x weight in kg x 0.8572 x serum creatinine in mg/ dL; Male creatinine clearance = (140 age in years) x weight in kg x 1.0072 x serum creatinine in mg/dL.
- Because the teratogenicity of cetuximab is not known, the patient, if sexually active, must be postmenopausal, surgically sterile, or using effective contraception (hormonal or barrier methods).
- Female patients of childbearing potential must have a negative serum pregnancy test within 7 days prior to enrollment.
- Ability to understand and the willingness to sign a written informed consent document.

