6.1.2. Notes on progression and new lesions

- For equivocal findings of progression (e.g. very small and uncertain new lesions; cystic changes or necrosis in existing lesions), treatment may continue until the next scheduled assessment. If at the next scheduled assessment, progression is confirmed, the date of progression should be the earlier date when progression was suspected.
- 2. A previous abnormal target lymph node that became normal and subsequently enlarged in size meeting the criteria for a pathologic and measurable lymph node (a short axis of ≥1.5 cm) should be added to the sum of diameters to determine if criteria for progression are met based on target lesions.
- A previously abnormal non-target lymph node that became normal and subsequently recurred must meet the criteria for progression based on non-target lesions to be considered progression.
- 4. A normal lymph node at baseline (<1.0 cm) that subsequently becomes pathologic is considered a new lesion and should be considered progression.
- 5. If newly abnormal lymph node(s) of unclear etiology is driving the progression event, continuation of treatment/follow-up and confirmation by a subsequent exam should be contemplated. If it becomes clear that the new lymph node has not resolved, is not resolving, or has increased in size, the date of progression would be the date the new lymph node was first documented as meeting pathologic criteria.

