14. APPENDICES

14.1 APPENDIX 1: TUMOR RESPONSE ASSESSMENT ACCORDING TO RECIST 1.1

Response criteria for target lesions

Study Number: MCC 19178 IND#: Exempt

1.	Complete Response (CR):	Disappearance of all target lesions. Any pathological lymph nodes (whether target or non-target) must have a reduction in short axis to < 10 mm).
2.	Partial Response (PR):	At least a 30% decrease in the sum of diameters of target lesions, taking as reference the baseline sum diameters.
3.	Progression (PD):	At least a 20% increase in the sum of diameters of target lesions, taking as references the smallest sum on study (this includes the baseline sum if that is the smallest on study). In addition to the relative increase of 20%, the sum must also demonstrate an absolute increase of at least 5 mm (note: the appearance of one or more new lesions is also considered progression).
4.	Stable Disease (SD):	Neither sufficient shrinkage to qualify for PR nor sufficient increase to qualify for PD, taking as references the smallest sum diameters while on study.

Response criteria for non-target lesions

1.	Complete Response (CR):	Disappearance of all non-target lesions and normalization of tumor marker level. All lymph nodes must be non-pathological in size (< 10 mm short axis).
2.	Non-CR/Non-PD:	Persistence of one or more non-target lesion(s) or/and maintenance of tumor marker level above the normal limits.
3.	Progression (PD):	Unequivocal progression of existing non-target lesions (note: the appearance of one or more new lesions is also considered progression).

Overall response

Target lesions	Non-Target lesions	New lesions	Overall response
CR	CR	No	CR
CR	Non-CR/Non-PD	No	PR
CR	Not evaluated	No	PR
PR	Non-PD or not all evaluated	No	PR
SD	Non-PD or not all evaluated	No	SD
Not all evaluated	Non-PD	No	NE
PD	Any	Yes or No	PD
Any	PD	Yes or No	PD
Any	Any	Yes	PD

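### Section 6.1.1 and Appendix 1 define target-lesion progression differently (5 mm minimum, place of baseline in the reference) and no text says which governs; on-treatment scan fields also differ

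*Combined protocol and SAP*

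**What the plan says.** Section 6.1.1 gives this progression rule for target lesions: "At least a 20% increase in the sum of the longest diameters of target lesions, taking as reference the smallest sum longest diameter recorded". The sentence goes on to count that smallest sum from the baseline measurements, without saying whether the baseline sum is itself a candidate. A new lesion is also progression. No absolute increase is required.

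Appendix 1, titled as RECIST 1.1, uses the same 20% and adds: "In addition to the relative increase of 20%, the sum must also demonstrate an absolute increase of at least 5 mm". It states that the baseline sum is included in the reference if it is the smallest on study.

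Section 6.1 is headed as RECIST criteria but names no version and does not point to Appendix 1. Section 3.3.2 cites version 1.1 only for measurable disease. The notes on progression (the second section numbered 6.1.2) deal with equivocal findings and lymph nodes. For equivocal findings later confirmed, "the date of progression should be the earlier date when progression was suspected". They do not supply the 5 mm rule.

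On the scan field, the Study Calendar's tumor-measurement footnote says "Scans in screening will include: CT- or MRI-neck, CT-chest, CT-abdomen, and CT-pelvis" and then "Response scans can be limited to the anatomy of areas of known and suspected disease". Footnote n, on the on-treatment cell of the same row, sets the scan times while on study drugs "and will include: CT- or MRI-neck, CT-chest, CT-abdomen, and CT-pelvis". Section 3.2.1 names only the neck.

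**The concern.** A site that follows the efficacy section as written and a site that follows the appendix can classify the same measurements differently. The call has two consequences. Under Section 3.3.4 progression ends protocol therapy, and under Section 10.1.2 progression enters the Kaplan-Meier estimates of median and 1-year PFS.

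Central review (Section 6.2) does not settle it. Images are evaluated for all evaluable patients at the coordinating site. The two outside sites send images only from patients with a response, in order to confirm the response. Progression at those sites is therefore not checked centrally.

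The scan field matters because a new lesion is progression by itself. A limited scan can miss one outside the imaged area, which would make the progression date later.

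**Working it through.** The plan states no figure on this point, so there is nothing to reproduce. The check compares the two rules.

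**5 mm minimum.** Let N be the nadir sum in mm.

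- Section 6.1.1 threshold: 1.2 × N.
- Appendix 1 threshold: the larger of 1.2 × N and N + 5.
- They differ when 0.2 × N < 5, that is N < 25 mm. The gap is 5 − 0.2 × N.

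| Nadir (mm) | Section 6.1.1 (mm) | Appendix 1 (mm) | Gap (mm) |
|---|---|---|---|
| 15 | 18.0 | 20.0 | 2.0 |
| 20 | 24.0 | 25.0 | 1.0 |
| 24 | 28.8 | 29.0 | 0.2 |
| 25 | 30.0 | 30.0 | 0 |

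Section 6.1 asks for centimetres without stating the precision. If sums are recorded to 0.1 cm (an assumption), the first recordable sums reaching +20% from nadirs of 21, 22, 23 and 24 mm are 26, 27, 28 and 29 mm. These equal N + 5, so the rules then differ only at nadirs of 20 mm or less.

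**Can such nadirs occur?** Yes. Entry needs only "at least one lesion that can be accurately measured in at least one dimension", and the progression notes describe a node as "meeting the criteria for a pathologic and measurable lymph node (a short axis of ≥1.5 cm"), so a single-node baseline of 15 mm is possible. Shrinkage also leads there:

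- After a 30% decrease, N < 25 mm when baseline < 25/0.7 = 35.7 mm. For N ≤ 20 mm, the limit is 20/0.7 = 28.6 mm.
- After a 50% decrease, the limits are 25/0.5 = 50 mm and 20/0.5 = 40 mm.

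**Baseline in the reference.** Take sums of 50 mm at baseline, 58 mm at week 6 and 62 mm at week 12.

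- Week 6: 58/50 = 1.16, not progression under Appendix 1.
- Week 12, Appendix 1: the reference is 50 mm; 62/50 = 1.24 and the increase is 12 mm. This is progression.
- Week 12, Section 6.1.1 read as excluding baseline: the reference is 58 mm; 62/58 = 1.069. This is not progression.

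On that reading Section 6.1.1 is the later rule, at sums well above 25 mm.

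**Size of a date shift.** Footnote n puts scans at C2D15, C4D1, C6D1 and C9D1, which are weeks 6, 12, 20 and 32 from C1D1. A call made one scan later moves the date by 6, 8 or 12 weeks depending on when it occurs. Whether a scan falls between the two thresholds depends on tumor growth, which the documents do not give.

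**Scan field.** Section 4.2.4 describes the on-treatment scans as the assessment of radiological response. The tumor-measurement footnote's wording on response scans therefore reaches the same scans as footnote n.

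**The case against.** The strongest reply is that intent is not in real doubt. The section is headed RECIST, the only version named anywhere is 1.1, and Appendix 1 holds the only overall-response table. That stands as to likely intent. It does not supply the missing cross-reference, and Section 6.1.1 is the text an assessor meets first.

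Footnote n is also the more specific and mandatory rule, and the limited-field wording may have been meant for other scans, such as the end-of-treatment scan, for which footnote o sets no field. This stands in large part and makes the scan-field conflict the lesser half of the point. The permissive footnote also covers suspected as well as known disease, which limits what could be missed. Section 3.2.1 sits under the phase I heading, but phase I patients treated at the MTD count in phase II.

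The 5 mm difference affects only calls made on target-lesion growth, without a new lesion or non-target progression. If a site treats a small increase as equivocal and later confirms it, back-dating under the progression notes removes the date shift.

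Two stronger inferences fail. A reader might conclude that Section 6.1.1 can only bring progression earlier, and only below 25 mm. That is true of the 5 mm rule alone; the baseline wording can act the other way at larger sums. A reader might also assume that each affected patient's date moves by a full scan interval. That requires a scan to fall between the thresholds, and the documents give no growth rate from which to say how often it would.

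**Conclusion.** The point holds as an inconsistency in current text that should be corrected. Without the 5 mm minimum, Section 6.1.1 as written makes progression calls that Appendix 1 would not, by up to 2 mm at nadirs from 15 mm to just under 25 mm. The zone ends at 20 mm if sums are in whole millimetres. The delaying effect depends on reading the baseline sum as excluded. That reading is open but not the natural one, since the first on-treatment scan would then have nothing to be compared with.

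No net direction or size for median or 1-year PFS can be stated, because the documents give no distribution of tumor burden and no growth rates. PFS is secondary and carries no test. A reader might infer that the main efficacy conclusion is at risk. It is not: the primary endpoint is overall survival, and neither it nor the 45 and 43 patients planned depends on the progression rule.

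**What to change.** State in Section 6.1 that Appendix 1 (RECIST 1.1) governs CR, PR, SD and PD. Replace the response definitions in Sections 6.1.1 and 6.1.2 (Non-Measureable Lesions) with a reference to it, and keep the notes on progression. This also removes the mixed use of measurable and target lesions, the different CR rule for nodes, and the 6- versus 8-week minimum for stable disease. Appendix 1 gives no such minimum, so state one once if it is wanted.

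State that on-treatment scans follow footnote n, and align the tumor-measurement footnote and Section 3.2.1 to it.

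The response criteria cost only wording. Any site now using limited scans would image more anatomy, which footnote n already requires.
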